## **2. Objectives/Specific Aims**

**Aim 1:** Fluoxetine treatment begun early after COVID-19 infection will reduce hospitalizations, intubations, and death from COVID-19 and complications more than no medication

**Aim 2:** Fluoxetine will decrease intubations and mortality in patients hospitalized with COVID-19 infection greater than no medication.

**Aim 3 :** Fluoxetine treatment of COVID-19 infected patients will not cause significant side effects or increase morbidity and mortality compared to no medication

**Aim 4.** Collect blood samples from 40 subjects for future cytokine analysis: both subjects taking fluoxetine and not taking fluoxetine samples taken at baseline and weekly after study initiation.

[figure not shown]

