#### b) **Method of treatment assignment**

Single arm patient centered clinical trial

At study entry, participants will consent study participation via daily monitoring and will choose whether to participate in the activity monitoring, cytokine assessment and drug treatment portions of the trial. Participants who do not choose to take fluoxetine will serve as the control subjects. Additionally, patients will have the choice weekly to decide to start, continue, or discontinue the fluoxetine. See figure below :

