#### c) **Inclusion/exclusion criteria**

Inclusion : Patients aged 18 and above, able to give informed consent

COVID-19 test positive or presumptive positive awaiting COVID testin or results by following criteria: fever, cough and shortness of breath

Overall Study Exclusion Criteria :

Unable to give informed consent  
Prisoner/ institutionalized patient  
Under age 18

Exclusion from Fluoxetine Arm:

Active bleeding requiring blood products  
Bipolar disorder not on mood stabilizing medication\*  
Known allergy or hypersensitivity to fluoxetine  
Currently taking the following medications : MAO I, pimozide, thioridine  
Currently taking hydroxychloroquine  
Pregnant or breastfeeding (pregnancy questionnaire attached)  
For hospitalized patients : QTc greater than 500 ms  
\*Hospitalized patient may be on hydroxychloroquine if QTc<500 and the primary attending approves

Exclusion from Blood Sample Provision:

Pregnant  
Self-report of under 110 pounds

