#### **Aim 1 : Hospitalization rates**

Assumptions:

1. 2/3 of patients who enter the trial will choose to take fluoxetine
2. 10% of COVID-19 + patients will progress to a clinical condition requiring hospitalization
3. Fluoxetine treatment decreases hospitalization rate by 50%

Sample Size : 312 in the no medication group and 624 in the 2 fluoxetine groups, for a total sample size of 936. This sample size is very achievable given the current coronavirus pandemic.

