#### **4) Planned data analysis**

Aim 1, 2, 3 : Descriptive statistics,

Compare rates of primary and secondary outcome measures in subjects receiving fluoxetine with those not receiving fluoxetine by Student t-test and Chi-square test as appropriate.

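### Aim 1 asks whether fluoxetine reduces hospitalization, but the only planned comparison of the self-selected groups is unadjusted, although prognostic variables are collected at entry

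*Combined protocol and SAP*

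**What the plan says.** All references are to the combined protocol and SAP.

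- **Objective (section 2).** Aim 1 states that fluoxetine begun early "will reduce hospitalizations, intubations, and death from COVID-19 and complications more than no medication". Section 3f makes hospitalization the Aim 1 primary outcome.
- **Assignment (section 3b).** There is no randomisation. "Participants who do not choose to take fluoxetine will serve as the control subjects", and "patients will have the choice weekly to decide to start, continue, or discontinue the fluoxetine".
- **Eligibility (section 3c).** A list headed "Exclusion from Fluoxetine Arm" bars some patients from the drug but not from the study. One entry reads "For hospitalized patients : QTc greater than 500 ms", so inpatients can enrol; section 3e also lists the hospital as a setting.
- **Sample size (section 3d).** The plan assumes that "2/3 of patients who enter the trial will choose to take fluoxetine" and arrives at "312 in the no medication group and 624 in the 2 fluoxetine groups, for a total sample size of 936", for 10% vs 5% hospitalized, alpha 0.05 and power 0.80.
- **Analysis (section 4).** For Aims 1 to 3 the plan is descriptive statistics plus a comparison of outcome rates "in subjects receiving fluoxetine with those not receiving fluoxetine by Student t-test and Chi-square test as appropriate".
- **Data collected (sections 3g and 3h).** Demographics, medical history, comorbidities, medications and symptom duration are listed as variables. The baseline form, symptom checklist, PHQ-9 and GAD-7 are completed at entry.
- **Timeline.** Fluoxetine enrolment closes on 2/1/2021, overall enrolment on 4/1/2021.

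**The concern.** A chi-square test of choosers against decliners is a valid test of association. It tests a drug effect only if the two groups would have had the same hospitalization risk without the drug. Self-selection gives no assurance of that, and the plan neither states the assumption nor checks it. No section provides for regression, stratification, matching, weighting or a sensitivity analysis for confounding. The qualifier about appropriateness in section 4 only chooses between two unadjusted tests.

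The composition of the control group adds to this. Read literally, patients not receiving fluoxetine include those barred from it and those enrolled after its arm closed. The plan does not say whether they count as controls.

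Aim 1 is the one comparison that the protocol sizes as achievable. As planned, a significant result could reflect who chose the drug, and a null result could hide a real benefit.

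**Working it through.** **1. The plan's own figure.** Inputs from section 3d: p1 = 0.10, p2 = 0.05, ratio 1:2, alpha 0.05, power 0.80. Sidedness is not stated; two-sided reproduces the figure. Pooled risk p = (0.10 + 2 × 0.05)/3 = 0.0667.

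n1 = [1.96 √(1.5 p(1−p)) + 0.842 √(p1(1−p1) + p2(1−p2)/2)]² / 0.05² = 311.6, so 312 + 624 = 936, an exact match.

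Power = Φ((|d| − 1.96 SE0)/SE1), with SE0 pooled and SE1 unpooled. Here Φ((0.05 − 1.96 × 0.01730)/0.01909) = 0.800. The arithmetic is sound.

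**2. Unequal prognosis, no drug effect.** All inputs here are assumptions except 312/624 and the 10% risk, which is applied overall. One binary trait has prevalence 0.30 and risk ratio RR; uptake is uT with the trait and uN without.

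- Risk without the trait: b = 0.10/(0.70 + 0.30 RR)
- Overall uptake: u = 0.30 uT + 0.70 uN, held near 67%
- Trait share: 0.30 uT/u in choosers, 0.30(1 − uT)/(1 − u) in decliners
- Group risk: b(1 + share × (RR − 1))

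Example, uT = 0.50, uN = 0.74, RR = 3: b = 0.0625 and u = 0.668. Shares are 0.2246 and 0.4518, and risks are 9.06% in choosers and 11.90% in decliners. Rejection is Φ((0.0284 − 1.96 × 0.02080)/0.02163) = 28.4%; the other tail is negligible.

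Two-sided false-positive rate of the crude test:

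| Uptake with / without trait | RR 1.5 | RR 2 | RR 3 |
|---|---|---|---|
| 60% / 70% | 5.6% | 6.7% | 9.2% |
| 55% / 72% | 6.6% | 9.6% | 17.0% |
| 50% / 74% | 8.0% | 14.0% | 28.4% |

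**3. Opposite direction, true halving of risk.** With uptake 83.4% / 59.6%, the crude difference shrinks from 5.0 points to 4.2, 3.6 and 2.7 points for RR 1.5, 2 and 3. Power falls from 80% to 67%, 55% and 36%.

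**4. Does adjustment repair it?** Simulation used 3,000 replicates at n = 936, with inverse-probability weighting on a seven-term propensity score (the trait plus six noise covariates). With no effect and uptake 50% / 74%, crude error was 7.7% / 15.4% / 27.3% and weighted error 4.4% / 6.2% / 5.6%. In the case of step 3, the mean weighted difference was −5.0 points, the true value. A separate simulation with other assumptions (10% control risk, trait in 40% of decliners and 20% of choosers, RR 3) gave 21.6% crude and 5.1% with Mantel-Haenszel stratification.

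**5. Power of the adjusted analysis.** For a risk difference with an unpooled 95% CI, power = Φ(0.05/SE − 1.96), SE = √(0.09/n1 + 0.0475/n2). If covariates explain a share R² of treatment choice (assumed 5% to 20%), SE is divided by √(1 − R²). With even enrolment (assumed), 936 × 306/365 = 785 patients enter while the fluoxetine arm is open. That is 262/523 at two-thirds uptake, or 161/624 if all 624 fluoxetine patients are reached (785 − 624 = 161).

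| n1/n2 | SE | Power before adjustment | R² 5% to 20% |
|---|---|---|---|
| 312/624 | 0.01909 | 74% | 72% to 65% |
| 262/523 | 0.02084 | 67% | 65% to 57% |
| 161/624 | 0.02520 | 51% | 49% to 43% |

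Simulating the weighted analysis in the case of step 3 gave lower values: about 62% to 69% at 936 and 54% to 61% at 785. There R² is only 0.30 × 0.70 × 0.238²/(0.667 × 0.333) = 0.054, so the formula is itself somewhat optimistic.

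Expected events after the date restriction: 26.2 + 26.2 = 52 (262/523) or 16.1 + 31.2 = 47 (161/624).

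**The case against.** The strongest reply is that the size of the problem is wholly assumed. The documents give no trait prevalence, risk ratio or uptake difference. That stands: the mildest cells barely exceed 5%, and in the reverse case at RR 1.5 simulated crude and weighted power are the same (66.2% and 66.8%). A reader might infer that this trial's false-positive rate will lie between 6% and 28%, or that the bias will favour fluoxetine. The documents support neither; the grid shows the mechanism only. But equal prognosis is also an assumption, and the plan relies on it without saying so.

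Second, section 3a calls the design partly observational and section 3d uses the word pilot. Both soften the causal reading. However, an observational comparison is where adjustment is most needed. The pilot remark follows the Aim 2 calculation, and the sentence on qualitative use names Aims 3 and 4. Aim 1 is formally powered and its sample size is called achievable.

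Third, which non-recipients count as controls is strictly a separate question from adjustment. That is fair. A reader might infer that barred or late-enrolled patients will be counted as controls, but the plan is silent. The adjusted analysis still has to settle it.

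Fourth, analysing by choice at entry changes the comparison from receipt to initial decision. That stands as a cost.

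**Conclusion.** The point holds. Aim 1 is causal, the groups are self-selected, and the only planned test ignores prognostic variables that the study collects. The stated error rate and power apply to a drug effect only under equal prognosis.

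The illustrative range (6% to 28% false positives, or power down to 36%) rests on the assumed trait, risk ratios and uptake differences, and other assumptions would give other ranges.

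Three stronger readings are not supported. The sample-size arithmetic is not wrong: 936 reproduces exactly. The chi-square is not invalid as a test of association. Adjustment would not make the result causal, since unmeasured confounding remains.

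Nor should a reader infer that adjustment is nearly free. Shrinking the pooled z-test by the same R² range would suggest 78% to 71% at 936, but that is too optimistic for a risk difference with a 95% CI.

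**What to change.** Make the primary Aim 1 analysis a prespecified covariate-adjusted comparison of hospitalization by the fluoxetine choice made at entry.

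- **Covariates:** age, sex, comorbidities, concomitant medications, confirmed vs presumptive COVID status, baseline symptoms and their duration, PHQ-9 and GAD-7. Section 3g counts symptom days up to testing; count them to study entry.
- **Method:** propensity-score weighting is one suitable choice, because 47 to 52 events are too few for a logistic outcome model with the full list. Stratification or matching on the score is also acceptable.
- **Population:** patients not hospitalized at entry, eligible for fluoxetine, and enrolled while its arm was open.
- **Reporting:** adjusted risk difference with 95% CI and covariate balance. Keep the crude chi-square as descriptive. Call the result an adjusted non-randomised association. State that the 80% power applies only to the crude pooled comparison of 312 vs 624.
- **Timing:** fix the method and covariates before outcomes are examined by group. The timeline starts data analysis and board reviews on 7/1/2020.

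No new visits or patients are needed. The cost is analysis work and the lower power shown in step 5 of the working. Two further losses cannot be sized from the documents: excluding ineligible patients and those hospitalized at entry, and dilution of the effect of taking the drug when patients start or stop after entry.

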**Prevention of Hospitalization**

Hospitalization, no medication	10%
Hospitalization, Fluoxetine	5%
Alpha	0.05
Beta	0.2
Power	0.8
Sample Size	
No medication	312
Fluoxetine, low or high	624
Total	936

Aim 2 : Intubation in those hospitalized

Assumptions

1. 10% of patients requiring hospitalization for COVID-19 + will progress to intubation
2. Fluoxetine treatment decreases intubation rate by 20%

Aim 2: Death in those hospitalized

Assumptions

1. 1% of patients requiring hospitalization for COVID-19 + will die during that hospitalization
2. Fluoxetine treatment decreases mortality rate by 20%

**Sample Size** : 3213 in the no medication group and 3213 in the fluoxetine groups, for a total sample size of 6426. These sample sizes will not be achievable in this pilot study. Data from Aims 3 and 4 will therefore be used qualitatively for the gathering of pilot data.

Prevention of intubation, death	
Sample Size	
No medication	3213
Fluoxetine	3213
Total	6426
Prevention of Intubation	

Intubation, death in no medication	10%
Intubation, death in fluoxetine	8%
Alpha	0.05
Beta	0.2
Power	0.8

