**f) Primary and secondary outcome measures**

Primary Outcome Measures:

Aim 1 : Rates of Hospitalization

Aim 2 : Rates of Intubation and Death

Aim 3 : Side effect profile

Secondary Outcome Measures:

Aim 1 and 2 : Depression, Anxiety, Suicidal thinking, Days of Illness, Severity of Illness

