**h) Procedures, interventions, schedule**

Week/Day	Patient Intervention	Setting/ Responsible Individual	Standard of Care	Research Purposes Only
1/1	Informed Consent	Phone/ research team	-----	Yes
1/1	Baseline Study Data	Phone/ research team		Yes
1	Blood Sample	Laboratory Services	Inpatient	outpatient
1	Physician Interview/ Medication Prescription	Phone/Study physician	----	Yes
Daily	Symptom/ Side effect Check In	Phone/ research team		Yes
Weekly	Physician Interview/ Medication Prescription	Phone/Study physician	----	Yes
Weekly or Change in Clinical Status*	Blood Sample	Laboratory Services	Inpatient	outpatient

\*Change in Clinical Status includes outpatient to inpatient, transfer to ICU, and intubation

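### Fluoxetine use can change every week, but the Aim 3 side-effect comparison is by subject, with no on-drug time and no rule for switchers

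*Combined protocol and SAP*

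**What the plan says.** Section 3b builds switching into the design: "patients will have the choice weekly to decide to start, continue, or discontinue the fluoxetine". A restart is not named, but a weekly choice allows one. The same section defines the comparator: "Participants who do not choose to take fluoxetine will serve as the control subjects".

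Section 3f lists "Aim 3 : Side effect profile" among the primary outcomes. The aim in section 2 is that fluoxetine "will not cause significant side effects or increase morbidity and mortality compared to no medication".

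Apart from descriptive statistics, section 4 gives one method for Aims 1 to 3, a comparison of rates "in subjects receiving fluoxetine with those not receiving fluoxetine by Student t-test and Chi-square test as appropriate". It mentions no person-time, on-drug window or rule for a participant who changes.

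The section 3h schedule has a daily "Symptom/ Side effect Check In" and a weekly physician contact for prescribing. Section 3g lists medications as a variable. Intended exposure can therefore be assigned week by week. The visible text describes no record of doses actually taken.

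**The concern.** Side effects are collected daily and exposure can change weekly, but the test gives each person one label. A switcher's events or time must then fall partly on the wrong side:

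- **Groups by entry choice.** On-drug side effects of people who start later count as control events, and the drug-free time of people who stop counts as fluoxetine time.
- **Groups by ever/never use.** Off-drug time before a start and after a stop counts as fluoxetine time.

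Where risk persists during use, either rule pulls the two rates together. In an efficacy comparison that would be conservative. In Aim 3 the hoped-for result is no excess of side effects, so a diluted difference favours the claim.

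**Working it through.** **The plan's own figure.** Section 3d gives "312 in the no medication group and 624 in the 2 fluoxetine groups" for Aim 1, from 10% against 5%, power 0.80 and alpha 0.05. With allocation ratio k = 2, two-sided alpha and pooled variance under the null:

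- mean risk = (0.10 + 2 × 0.05)/3 = 0.0667
- n = [1.960 × √(1.5 × 0.0667 × 0.9333) + 0.842 × √(0.09 + 0.0475/2)]² / 0.05² = (0.599 + 0.284)² / 0.0025, which gives 312 before final rounding, and 2 × 312 = 624

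The figure reproduces and is not disputed. No sample size or power is stated for Aim 3.

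**Inputs for Aim 3.** Group sizes of 312 and 624 are borrowed from Aim 1. Everything else is assumed, because the documents give no side-effect risks, switching share or follow-up length:

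- risk r0 = 10% off drug and r1 = 17% on drug, so d = 0.07
- a share c of controls starts later, and the same share of the fluoxetine group stops
- one switch per switcher, spread evenly over weeks 1 to 7 of 8 (8 weeks is the blood-draw period in section 3h)

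Power = Φ[(difference − 1.960 × s0)/s1], where s0 is the pooled and s1 the unpooled standard error. With no switching, s0 = 0.02453 and s1 = 0.02268, so power = Φ[(0.07 − 0.04808)/0.02268] = Φ(0.966) = 83.3%.

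**Case A: risk persists while on drug.** A switcher spends on average half of follow-up on drug, since the mean of 1/8 to 7/8 is 1/2. The switcher's risk is therefore 0.10 + 0.035 = 0.135. A 4-week period with switches at weeks 1 to 3 has the same mean and gives the same result.

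- Entry choice: control risk = 0.10 + 0.035c and fluoxetine risk = 0.17 − 0.035c, so the difference is 0.07(1 − c).
- Ever/never: control risk stays at 0.10 in 312(1 − c) subjects. Fluoxetine risk = [624(0.17 − 0.035c) + 312c × 0.135]/(624 + 312c). At c = 10% this is (103.896 + 4.212)/655.2 = 0.165, a difference of 0.065, or 93% of 0.07.

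**Case B: side effects come only soon after starting.** Stoppers have already had theirs, and each later starter carries the full 17%.

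- Entry choice: control risk = 0.10(1 − c) + 0.17c, so the difference is again 0.07(1 − c).
- Ever/never: later starters move to the fluoxetine group and the difference stays at 0.07. Power falls only because the control group is smaller.

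| Case and grouping | Difference kept at c = 5 / 10 / 20% | Power at c = 5 / 10 / 20% |
|---|---|---|
| A, entry choice | 95 / 90 / 80% | 79.2 / 74.6 / 64.0% |
| A, ever/never | about 96 / 93 / 86% | about 79.5 / 75.2 / 65.7% |
| B, entry choice | 95 / 90 / 80% | 78.8 / 73.7 / 62.2% |
| B, ever/never | 100 / 100 / 100% | 82.2 / 80.9 / 77.6% |

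The shares of 5, 10 and 20% of 312 are about 16, 31 and 62 controls.

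**Sensitivity to the assumed risks** (case B, entry choice):

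- 5% against 10%: power falls from 76.5% to 71.2 / 65.6 / 53.9%.
- 10% against 20%: power falls from 98.3% to 96.9 / 94.9 / 87.9%.

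**The case against.** **The ever/never reading fits the text at least as well.** Someone who starts in week 3 has chosen the drug and is receiving it. Under that reading no later starter stays in the control group, and with early-onset side effects the difference is not diluted. Events before a late start would then be charged to fluoxetine, which works against the safety claim. This stands. A reader might infer that the comparison is biased toward safety however it is carried out, or that later starters are the main leak. The documents support neither, because they do not fix the grouping and give no timing of side effects.

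**Exposure is partly recorded.** Prescribing is reviewed weekly and medications are a listed variable, so it would be too strong to say that exposure is unknown. Two items are also not visible: the figure that section 3b points to, which may show how switchers are grouped, and the check-in form, which may already ask about doses. If the form does, only the analysis point remains.

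**Aim 3 may be only descriptive.** Section 3d says: "Data from Aims 3 and 4 will therefore be used qualitatively for the gathering of pilot data". That sentence follows the Aim 2 sample size and may be a numbering slip, since section 4 names Aim 3 for the comparison. Even if it is meant literally, a description by on-drug time is more informative than one by a fixed label.

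**The inputs are chosen.** No power is claimed for Aim 3, and larger effects lose little power at 5 or 10% switching. This also stands.

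**Conclusion.** The concern holds as a minor one. Section 4 applies a fixed-label comparison to an exposure that section 3b lets participants change weekly, and it says neither how switchers are labelled nor how on-drug time enters.

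If risk persists during use, both natural groupings shrink the difference, to between 80 and about 96% of its true size when 5 to 20% of each group switch. Power then falls from 83.3% to between 64.0 and about 79.5%. If side effects come only early, the loss depends on the grouping: similar by entry choice, small by ever/never.

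These figures illustrate a mechanism. They do not estimate this trial's bias and are not upper bounds. They rest on assumed risks, assumed switching shares, a single switch per person and group sizes borrowed from Aim 1. A reader might take the power losses as a demonstrated defect of Aim 3, but the documents give no side-effect rates or switching share from which to show that.

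**What to change.** In section 4, for Aim 3 only and beside the group comparison:

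1. State which group a switcher joins.
2. Report side effects by on-drug and off-drug time, using the weekly prescription record. If the daily check-in form lacks it, add one yes/no question on whether study fluoxetine was taken since the last call.
3. Count each new-onset side effect once per episode, so that a persistent effect is not counted every day.
4. Treat a day as on drug if a dose was taken that day or in the previous 7 days, and repeat with 0. The 7 days are an assumption. For example, doses on days 1–7 and 22–28 give 21 days on and 7 off with the 7-day rule, and 14 and 14 with 0.
5. Give a rate ratio with 95% CI from a Poisson model with errors clustered by participant, adjusted for week since entry, because illness symptoms recorded at the same call change over time.
6. Split on-drug time into the first weeks after starting and later, with the cut-off fixed in advance, so that long tolerated use does not hide early effects.

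The cost is at most one question in a call already made daily, one table and one sentence on grouping. Dose-taking would be self-reported and use is self-selected, with later on-drug time weighted toward people who tolerate the drug. The table therefore supports the group comparison and does not replace it.

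### The Aim 3 comparison has no eligibility limit, so patients barred from fluoxetine at entry count as non-receivers while barred, which by itself would make any bleeding or rhythm excess in takers look smaller

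*Combined protocol and SAP*

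**What the plan says.** Section 3 c) of the combined protocol and SAP has two relevant lists. The overall study exclusions are three: inability to consent, being a prisoner or institutionalized, and age under 18. A separate list, headed "Exclusion from Fluoxetine Arm", includes "Active bleeding requiring blood products" and "For hospitalized patients : QTc greater than 500 ms". Patients with either condition may therefore enrol but may not take the drug.

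Section 3 b) defines the comparison group by choice: "Participants who do not choose to take fluoxetine will serve as the control subjects". It also lets patients start, continue or stop fluoxetine each week. Section 4 defines the groups by receipt. For Aims 1, 2 and 3 it compares outcome rates "in subjects receiving fluoxetine with those not receiving fluoxetine" by t-test or chi-square test, with no adjustment and no restriction to patients eligible for the drug.

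Aim 3 (section 2) is that fluoxetine "will not cause significant side effects or increase morbidity and mortality compared to no medication". Section 3 f) gives its outcome only as the side effect profile. The sample size text in section 3 d) adds: "Data from Aims 3 and 4 will therefore be used qualitatively for the gathering of pilot data".

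**The concern.** Takers are screened for two conditions closely related to bleeding and rhythm harms; non-takers are not. If patients barred at entry have a higher rate of these events than eligible patients, they raise the control rate for a reason unrelated to not taking fluoxetine. A real excess in takers then looks smaller than it is. Because Aim 3 is a claim of no added harm, this component leans toward the hoped-for conclusion.

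It differs from ordinary self-selection, which could push either way. It follows from which list the criteria are placed in, and for conditions present at entry it can be removed by restriction. What is at stake is mainly the descriptive safety rates that readers of a pilot study will rely on. The safety board would see the same rates if its three-monthly interim analyses use the section 4 groups, which the plan does not state.

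**Working it through.** **The plan's own figures.** The plan gives no rate, effect or sample size for Aim 3, so there is no Aim 3 figure to reproduce. The Aim 1 group sizes (section 3 d) are borrowed for scale, and they do reproduce. With 10% versus 5%, two-sided alpha 0.05, power 0.80 and 2:1 allocation, the pooled proportion is (0.10 + 2 × 0.05)/3 = 0.0667, and

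n(control) = [1.96 × √(0.0667 × 0.9333 × 1.5) + 0.8416 × √(0.09 + 0.0475/2)]² / 0.05² = 311.6, rounded up to 312.

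That gives 624 on fluoxetine and 936 in total, as stated.

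**Who falls where.** A patient with one of the two conditions at entry is not excluded from the study, cannot receive fluoxetine while the condition lasts, and so is a non-receiver under section 4. No section in the available text creates a third group.

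**Model.** Let r0 be the event rate in eligible non-takers, r1 the rate in barred patients, and q the share of controls barred at entry.

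- Control rate = r0 × (1 − q) + r1 × q
- Taker rate = 2.0 × r0 (assumed true risk ratio of 2.0)
- Apparent ratio = taker rate / control rate

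The direction is the same whenever r1 exceeds r0. All of r0, r1, q and the ratio of 2.0 are assumptions. With 312 controls, q = 1% is about 3 patients and q = 2% about 6.

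| r0 | q | r1 | Control rate | Taker rate | Apparent ratio |
|---|---|---|---|---|---|
| 1% | 1% | 10% | 0.99% + 0.10% = 1.09% | 2% | 1.83 |
| 1% | 1% | 20% | 0.99% + 0.20% = 1.19% | 2% | 1.68 |
| 1% | 2% | 10% | 0.98% + 0.20% = 1.18% | 2% | 1.69 |
| 1% | 2% | 20% | 0.98% + 0.40% = 1.38% | 2% | 1.45 |
| 5% | 1% | 10% | 4.95% + 0.10% = 5.05% | 10% | 1.98 |
| 5% | 1% | 20% | 4.95% + 0.20% = 5.15% | 10% | 1.94 |
| 5% | 2% | 10% | 4.90% + 0.20% = 5.10% | 10% | 1.96 |
| 5% | 2% | 20% | 4.90% + 0.40% = 5.30% | 10% | 1.89 |

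**Effect on what a reader would see.** Treat the counts as binomial with 624 takers and 312 controls, and sum exactly over all outcomes for the probability that the observed taker rate is no higher than the observed control rate. At a 1% base rate it is 12.3% with nobody barred, 15.2% to 18.7% at q = 1%, and 18.3% to 26.0% at q = 2%. At a 5% base rate it is 0.3% with nobody barred and at most 0.5% in the four cases above. The two-sided uncorrected chi-square test at a 1% base rate has only 17.6% power even with nobody barred, so in that setting the harm is to the descriptive rates more than to the test.

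**After restriction.** Limiting controls to patients eligible at entry sets q = 0, and the apparent ratio returns to 2.0 as far as this component is concerned.

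**The case against.** Several objections have force.

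- **Size.** The result depends heavily on the base rate. At 5% the distortion is slight, and with 0.5% barred at a 1% base rate the ratio is still 1.91 to 1.83. This stands, and it is why both base rates are shown. A reader might infer that a true doubling could vanish: with 5% of controls barred, a 20% barred event rate and a 1% base rate, the ratio is 1.03. Nothing in the documents supports a barred share that high; at a 5% base rate the same inputs give 1.74.
- **Scaling from hospitalization.** It is tempting to size the barred group from the Aim 1 assumption that "10% of COVID-19 + patients will progress to a clinical condition requiring hospitalization", or about 31 of 312 controls. Those patients are hospitalized after entry. A bar that arises then is not one present at entry, an at-entry restriction would not remove it, and new bleeding or QTc prolongation in a control is an ordinary control outcome. The documents do not give the number barred at entry; they only list the hospital among the settings.
- **Permanent controls.** A reader might infer that barred patients can never be anything but controls. The weekly choice in section 3 b) lets them start once bleeding stops or QTc falls, and they may then carry a higher risk into the receiver group. Section 3 c) also lets some inpatients on hydroxychloroquine with QTc under 500 ms take fluoxetine.
- **Control membership.** Section 3 b) speaks of those who choose not to take the drug, and barred patients had no such choice; the figure there is not available to us. Section 4 groups by receipt, however, and nothing removes barred patients from it. At the least, the two sections need reconciling.
- **Outcome.** Bleeding and rhythm events are not named, and no ECG or bleeding assessment is scheduled. The nearest item is complications, among the section 3 g) variables. The point is therefore conditional.
- **Qualitative use.** Taken at face value, the statement that Aim 3 data are used qualitatively weakens any concern about a test. Section 4 still prescribes tests for Aim 3, and descriptive rates are shifted in the same way.
- **A larger problem.** The comparison is self-selected and unadjusted. That is true, and this point does not resolve it.

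**Conclusion.** The point holds in a limited, conditional form. The plan as written screens receivers, but not non-receivers, for active bleeding and inpatient QTc above 500 ms. If such events enter the Aim 3 side effect and morbidity comparison, and if patients barred at entry have more of them than eligible patients, this component makes any excess in takers look smaller.

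Its size cannot be established from the documents. The illustrative range for a true ratio of 2.0 is 1.83 to 1.45 at a 1% base rate and 1.98 to 1.89 at a 5% base rate, so it runs from material to negligible. It rests on the assumed 1% to 2% of controls barred at entry and 10% to 20% event rate among them.

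A reader might go further and infer that the whole Aim 3 comparison is biased toward safety. The documents do not support that: self-selection among eligible patients and weekly switching could act either way, and the plan has no rule for classifying switchers. The change is still worth making, because the asymmetry is plain in the text and cheap to remove.

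**What to change.** In section 4:

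1. Make the Aim 3 comparison among participants with none of the section 3 c) fluoxetine-arm exclusions at entry.
2. Count only events that start after entry.
3. Report ineligible non-takers in a separate row.
4. Give the safety board the same table.

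The cost is two or three lines of text and a check of the fluoxetine-arm exclusions at entry for participants who decline the drug. No study procedure is added. The downsides are a slightly smaller control group and unknown QTc eligibility for controls without a routine ECG. Bars that first arise after entry, and self-selection among eligible patients, are not addressed.
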